### 4. STUDY DESIGN

#### 4.1. Overall Design

This is a Phase 1, randomized, double-blind, sponsor-open, placebo-controlled, single arm study to evaluate the PK, safety, and tolerability following a single dose of PF-06823859 (900 mg) in healthy Chinese participants.

#### Number of Participants

Approximately 12 participants will be enrolled into the study. Approximately 10 participants will be randomized to PF-06823859 and approximately 2 participants will be randomized to placebo.

If more than 2 participants discontinue or withdraw before completing at least the follow-up visit at Day 100, or if there are participants whose PK samples are considered to be non-evaluable with respect to the primary PK objective, additional participants may be enrolled upon alignment between the sponsor and the investigator such that approximate 10 participants could provide evaluable PK samples for no less than Day 100 follow-up visit. For participants whose PK samples are considered to be non-evaluable with respect to the primary PK objective, their PK sample collection will stop for ethic consideration.

Within 28 days of successful completion of the screening process, eligible participants will be enrolled and randomized to receive a single IV infusion of PF-06823859 or placebo. Participants will be admitted into the CRU approximately 1 day prior to dosing and are required to remain in the CRU through completion of Day 5 evaluations. Participants will return to the CRU for outpatient follow-up visits through Day 157.

ADA levels will be monitored from samples collected at the times specified in the [SoA](#). Samples found to be positive will be further evaluated for NAb. Participants with positive results may be requested to return for additional follow-up for up to approximately 3 months after the last scheduled follow-up visit.

No formal interim analysis will be conducted for this study. As this is a sponsor-open study, the sponsor will conduct unblinded reviews of the safety, PK, and immunogenicity data through Day 28 after treatment administration to preliminarily assess any ethnic differences between Chinese and non-Chinese to support China joining future global PF-06823859 clinical development.

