### **6.3. Measures to Minimize Bias: Randomization and Blinding**

#### **6.3.1. Allocation to Study Intervention**

Participants will be allocated manually and randomly assigned to receive study intervention from a central randomization scheme. Investigators will remain blinded to each participant's assigned study intervention throughout the course of the study. In order to maintain this blind, an otherwise uninvolved third party (for example, pharmacist) will be responsible for the preparation and dispensing of all study intervention according to the randomization schedule and assigned treatment for the individual participant.

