#### **6.3.2. Breaking the Blind**

The method for breaking the blind in this study will be manual. A sealed envelope that contains the study intervention assignment(s) for each participant will be provided to the investigator. The sealed envelope will be retained by the investigator (or representative) in a secured area. In case of an emergency, the investigator has the sole responsibility for determining if unblinding of a participant's treatment assignment is warranted. Participant safety must always be the first consideration in making such a determination. If the investigator decides that unblinding is warranted, the investigator should make every effort to contact the sponsor prior to unblinding a participant's treatment assignment unless this could delay further management of the participant. If a participant's treatment assignment is unblinded, the sponsor must be notified within 24 hours after breaking the blind. When the blinding code is broken, the reason must be fully documented and entered on the CRF.

Once the study is complete, all envelopes (sealed and opened) must be inventoried and retained until authorization for destruction has been provided.

This is an investigator- and participant-blind (sponsor open) placebo-controlled study. Blood specimens will be obtained from all participants for PK analysis to maintain the study blind at the investigator site. Only the investigator site staff and blinded study monitor, if assigned, will be blinded to study treatment. The blinded study monitor, if assigned, will remain blinded to treatment until all monitoring for the study has been completed. Specimens from participants randomized to placebo will not be routinely analyzed. To minimize the potential for bias, treatment randomization information will be kept confidential by Pfizer unblinded personnel and will not be released to the blinded investigator or blinded investigator site personnel until the study database has been locked or the investigator requests unblinding for safety reasons.

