### **9.2. Analysis Sets**

For purposes of analysis, the following analysis sets are defined:

Participant Analysis Set	Description
Safety Analysis Set	All randomized participants who received at least 1 dose of the study intervention
PK Concentration Set	All randomized participants who received at least 1 dose of study intervention and at least 1 concentration value is reported
PK Parameter Set	All randomized participants who received at least 1 dose of study intervention and at least 1 of the PK parameters is calculated
Immunogenicity Analysis Set	All randomized participants who received at least 1 dose of study intervention with at least 1 post-treatment anti-drug antibody determination

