2.2. Study Design

This is a Phase 1, randomized, double-blind, sponsor-open, placebo-controlled study to evaluate the PK, safety, and tolerability following a single dose of PF-06823859 (900 mg) in healthy Chinese participants.

Approximately 12 participants will be enrolled into the study. Approximately 10 participants will be randomized to PF-06823859 and approximately 2 participants will be randomized to placebo.

PFIZER CONFIDENTIAL

The official version of this form is located in the electronic document management system.

If more than 2 participants discontinue or withdraw before completing at least the follow-up visit at Day 100, or if there are participants whose PK samples are considered to be non-evaluable with respect to the primary PK objective, additional participants may be enrolled upon alignment between the sponsor and the investigator such that approximate 10 participants could provide evaluable PK samples for no less than Day 100 follow-up visit. For participants whose PK samples are considered to be non-evaluable with respect to the primary PK objective, their PK sample collection will be stopped for ethic consideration.

Within 28 days of successful completion of the screening process, eligible participants will be enrolled and randomized to receive a single IV infusion of PF-06823859 or placebo. Participants will be admitted into the CRU approximately 1 day prior to dosing and are required to remain in the CRU through completion of Day 5 evaluations. Participants will return to the CRU for outpatient follow-up visits through Day 157.

ADA levels will be monitored from samples collected at the times specified in the SoA. Samples found to be positive will be further evaluated for NAb. Participants with positive results may be requested to return for additional follow-up for up to approximately 3 months after the last scheduled follow-up visit.

No formal interim analysis will be conducted for this study. As this is a sponsor-open study, the sponsor will conduct unblinded reviews of the safety, PK, and immunogenicity data through Day 28 after treatment administration to preliminarily assess any ethnic differences between Chinese and non-Chinese to support China joining future global PF-06823859 clinical development.

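### Does stopping PK draws in participants judged non-evaluable undo the site blind that sampling everyone is meant to protect?

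*Protocol*

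**What the plan says.** Amendment 1 introduced the stop. In the protocol synopsis (1.1), section 4.1 (Number of Participants) and section 4.2, participants whose PK samples are considered non-evaluable for the primary PK objective are to have no further PK draws: "their PK sample collection will stop for ethic consideration". SAP 2.2 repeats it: "their PK sample collection will be stopped for ethic consideration". The same condition can lead to extra enrolment: "additional participants may be enrolled upon alignment between the sponsor and the investigator".

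Protocol 6.3.2 describes how the site is kept blind: "Blood specimens will be obtained from all participants for PK analysis to maintain the study blind at the investigator site". It adds: "Specimens from participants randomized to placebo will not be routinely analyzed". Section 6.3.1 states the aim: "Investigators will remain blinded to each participant's assigned study intervention throughout the course of the study". Section 8.4 allows sampling times to change but keeps the number of samples fixed.

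The sponsor is open. Under section 4.1, "the sponsor will conduct unblinded reviews of the safety, PK, and immunogenicity data through Day 28 after treatment administration", and section 9.4 allows unblinded review at other times.

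No analysis set supplies a meaning for non-evaluable. The PK Parameter Set in protocol 9.2 and SAP 4 requires only that "at least 1 of the PK parameters is calculated". The nearest text is SAP 5.3.1, which permits exclusion from the PK analysis after an event affecting the profile and gives known loss of drug during the infusion as its example.

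**The concern.** Section 6.3.2 protects the site blind by treating everyone alike at the needle, and the Amendment 1 sentence ends that equal treatment for some participants. The site takes the blood, so it sees who has been stopped. Neither 6.3.2 nor 8.4 has a matching exception, so for a stopped participant the site cannot follow every passage to the letter.

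Whether a stop tells the site anything depends on a criterion that the plan does not state. If the open sponsor judged evaluability from concentrations, placebo participants, who are not routinely assayed, could not be stopped, and a stop would mean active. If placebo participants were themselves classed as non-evaluable because they have no drug to measure, a stop would point the other way. The discussion of extra enrolment between the open sponsor and the blinded investigator looks like a second route.

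At stake is the investigator's blind for that participant. Safety and tolerability is a primary objective, and the investigator rates the intensity and causality of every AE (protocol 10.3.3).

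**Working it through.** **What a stop reveals.** The inputs are the planned allocation, 10 active and 2 placebo (protocol 4.1), and the probability of a stop in each arm, *a* for active and *p* for placebo. The documents give neither probability, so every value of *a* and *p* below is an assumption.

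- Before any stop: P(active) = 10/12 = 83.3%.
- After a stop: P(active | stop) = 10*a* / (10*a* + 2*p*).

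1. *Site-visible cause, alike in both arms* (*a* = *p*): 10/12 = 83.3%. Nothing is learned.
2. *Concentrations only, placebo unassayed* (*p* = 0): 10*a*/10*a* = 100%. The arm is revealed.
3. *Both routes.* With 5% in each arm from dosing events plus 5% from concentrations in the active arm: (10 × 0.10) / (10 × 0.10 + 2 × 0.05) = 1.0/1.1 = 90.9%. With 5% plus 20%: 2.5/2.6 = 96.2%.
4. *Every placebo participant stopped* (*p* = 1). With *a* = 5%: 0.5/2.5 = 20%. With *a* = 10%: 1/3 = 33.3%. With *a* = 20%: 2/4 = 50%. Zero would also require that no active participant is ever stopped.

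The information in a stop therefore runs from none to complete, and the text has to show which case applies.

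**Which case the text supports.**

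- The stop sentence does not distinguish the arms and does not mention concentrations.
- The only concrete cause given for an affected IV profile is drug loss during infusion (SAP 5.3.1). The site can see that, and it can happen in either arm: case 1.
- The stated purpose of the review through Day 28 is a preliminary look at ethnic differences. Deciding evaluability is not mentioned.
- Section 6.3.2 keeps allocation confidential from blinded site staff until database lock or a safety unblinding. Sections 8 and 8.4 withhold PK results that could unblind. Case 4 requires acting on allocation, and case 2 on withheld results, in a way that shows the site the arm. Both run against the intent of these sections.

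**What would be exposed if case 2 occurred.** If a stop followed a review of data through Day 28, the remaining follow-up is Day 29 to Day 157: (157 − 29)/(157 − 1) = 128/156 = 82.1% of post-dose days for that participant. It would be shorter if the review came later and longer if an earlier review under 9.4 led to the stop. Ratings made before the stop were made blind. PK parameters come from an assay. SAP 3.5.1 counts any event after the start of treatment as treatment-emergent, whatever its causality rating. No hypothesis is tested (protocol 9.1, SAP 5.1).

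**What continued draws would cost.** Each draw is about 3 mL (protocol 8.4), against about 335 mL planned (protocol 8). I read the PK row of the Schedule of Activities as 8 scheduled outpatient draws, though the extracted table is misaligned. If the decision came after confinement: 8 × 3 = 24 mL, and 24/335 = 7.2%. If it came after the Day 29 visit: 6 × 3 = 18 mL, and 18/335 = 5.4%. A decision during confinement would add to this.

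**The case for a change.** The case for amending is a serious one. The stop is mandatory, and 6.3.2 and 8.4 contain no exception. The safeguards in 8 and 8.4 bar the reporting of results; they do not mention an instruction to stop drawing that follows from results. The condition refers to PK samples being non-evaluable, which can be read as a judgement about concentrations. With about 2 placebo participants, revealing one of them would expose half the control arm. A definition and one sentence in 6.3.2 would cost little.

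The textual mismatch and the missing criterion stand. The harm is much less secure. It requires a concentration-based or allocation-based practice that no passage describes, carried out in a way that defeats the purpose of 6.3.2.

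The enrolment route is weaker still. The same agreement covers extra enrolment after more than 2 withdrawals, it concerns whether to enrol more people, and nothing requires naming a participant. Where the cause was visible at the bedside, the investigator already knows whom it concerns.

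The one change with real effect would be to continue draws, unassayed, in a concentration-based case. The volume is small, but it means taking blood of no use to the PK objective, which is what the plan's ethical reason is meant to avoid. Whether one participant's blind justifies that is a matter on which reasonable people differ.

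**Conclusion.** No change to the plan follows. The passages do not fit together perfectly and non-evaluable is undefined, but this is missing operating detail. The study team can fill it in keeping with the rest of the plan: judge evaluability on dosing or sampling events that the site can see, without reference to concentrations or allocation. On that footing a stop leaves P(active) at 83.3% and reveals nothing.

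In the worst active-arm case the site's expectation moves from 83.3% to 100%. What is exposed is intensity and causality ratings after the stop, mainly in the affected participant. The PK parameters, treatment-emergent counts and descriptive conclusions of this 10:2, sponsor-open study remain sound.

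This rests on two assumptions: that sponsor staff observe the confidentiality terms of 6.3.2, 8 and 8.4 when they instruct the site, and that stops are rare. The documents give no stop rate, so the second cannot be checked. If stops were in fact made from concentrations, the site blind for the affected participants would be lost, and their later AE ratings should be read as unblinded.

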#### **4.2. Scientific Rationale for Study Design**

This study is designed to characterize the PK, safety, and tolerability of PF-06823859 after single IV dose administration in healthy Chinese participants.

To date, no PK or safety data of PF-06823859 in Chinese are available. Although there is no expected relevant PK difference between Chinese and non-Chinese because monoclonal antibodies are generally known for the absence of ethnic differences in their distribution and elimination, similar to that of endogenous IgG, it is still important to characterize PK and establish safety in Chinese participants to support future PF-06823859 clinical development as well as drug registration in China. Information collected from this study allows comparison of PK and safety profiles of PF-06823859 in Chinese and non-Chinese participants.

Single-dose rather than repeated dosing is planned in the study due to the long PF-06823859 terminal half-life as well as the steady-state PK can be well predicted from single dose data based on information of Study C0251001. The study duration and frequency of each assessment were decided based on information of Study C0251001.

In order to sufficiently evaluate PK, safety, and tolerability of PF-06823859 in Chinese participants while at the same time considering the clinical practice and minimal necessity for PK evaluation, if more than 2 participants discontinue or withdraw before completing at least the follow-up visit at Day 100, or if there are participants whose PK samples are considered to be non-evaluable with respect to the primary PK objective, additional participants may be enrolled upon alignment between the sponsor and the investigator such that approximate 10 participants could provide evaluable PK samples for no less than Day 100 follow-up visit. For participants whose PK samples are considered to be non-evaluable with respect to the primary PK objective, their PK sample collection will stop for ethic consideration.

Assessment of clinical safety laboratory tests ([Appendix 2](#)), vital signs, 12-lead ECG, physical examinations, and AE monitoring will provide essential data to evaluate the safety and tolerability of PF-06823859. There is a potential risk of increased susceptibility to viral infections with IFN- $\beta$  blockade as with any antagonist of Type 1 interferon signaling (eg,

anti-IFNAR1, anti-IFN- $\alpha$ , JAK inhibitors). Viral monitoring will be conducted as a precautionary measure to ensure participant safety.

COVID-19 specific assessments have been incorporated to minimize the risks of COVID-19 related complications to participants and the study site personnel.

#### 4.2.1. Choice of Contraception/Barrier Requirements

Human reproductive safety data are not available for PF-06823859, but there is no suspicion of human teratogenicity based on the intended pharmacology of the compound. Therefore, the use of a highly effective method of contraception is required (see [Appendix 4](#)).

#### 4.3. Justification for Dose

The proposed single IV dose level is 900 mg. The dose is selected based on the safety and tolerability in Study C0251001 and the doses of the Phase 2 study (Study C0251002) that is ongoing in patients with DM, to compare safety and PK among Chinese and non-Chinese.

PF-06823859 dose of 900 mg has been selected to evaluate the PK, safety, and tolerability of PF-06823859 in healthy Chinese participants so that safety and tolerability can be examined in the dose range including the maximum potential dose in the planned global late phase studies. In the ongoing Phase 2 study (C0251002), PF-06823859 doses of CCI Q4W and CCI Q4W are being evaluated with the primary objective being to characterize the effect of PF-06823859 in DM patients.

CCI

Based on the above data, 900 mg is selected to evaluate PK, safety, and tolerability of PF-06823859 in healthy Chinese participants.

#### 4.4. End of Study Definition

The end of the study is defined as the date of the last visit of the last participant in the study.

A participant is considered to have completed the study if he/she has completed all periods of the study, including the last visit.

## 5. STUDY POPULATION

This study can fulfill its objectives only if appropriate participants are enrolled. The following eligibility criteria are designed to select participants for whom participation in the study is considered appropriate. All relevant medical and nonmedical conditions should be taken into consideration when deciding whether a particular participant is suitable for this protocol.

Prospective approval of protocol deviations to recruitment and enrollment criteria, also known as protocol waivers or exemptions, is not permitted.

### 5.1. Inclusion Criteria

Participants are eligible to be included in the study only if all of the following criteria apply:

#### Age and Sex:

1. Male and female participants must be 18 to 45 years of age, inclusive, at the time of signing the ICD.
  - Refer to [Appendix 4](#) for reproductive criteria for male ([Section 10.4.1](#)) and female ([Section 10.4.2](#)) participants.

#### Type of Participant and Disease Characteristics:

2. Male and female Chinese participants who are overtly healthy as determined by medical evaluation including medical history, physical examination, laboratory tests, and 12-lead ECG.
3. Participants who are willing and able to comply with all scheduled visits, treatment plan, laboratory tests, lifestyle considerations, and other study procedures.

#### Weight:

4. BMI of 19 to 27 kg/m^2 (inclusive); and a total body weight >50 kg (110 lb).

#### Informed Consent:

5. Capable of giving signed informed consent as described in [Appendix 1](#), which includes compliance with the requirements and restrictions listed in the ICD and in this protocol.

## 5.2. Exclusion Criteria

Participants are excluded from the study if any of the following criteria apply:

### Medical Conditions:

1. Evidence or history of clinically significant hematological, renal, endocrine, pulmonary, gastrointestinal, cardiovascular, hepatic, psychiatric, neurological, or allergic disease (including drug allergies, but excluding untreated, asymptomatic, seasonal allergies at the time of dosing).
2. History of HIV infection, hepatitis B, or hepatitis C; positive testing for HIV, syphilis, HBsAg, or HCVAb. Hepatitis B vaccination is allowed.

For hepatitis B, all participants must undergo testing for HBsAg, HBcAb, and HBsAb.

- Participants who are HBsAg positive will be excluded.
  - Participants who are negative for all 3 serology tests may be eligible.
  - HBsAg negative, HBcAb positive, and HBsAb negative participants are to be excluded from the study.
  - Participants who are HBsAg negative, HBcAb negative and HBsAb positive and provide documentation of prior HBV vaccination, may be eligible for the study and will not require HBV DNA monitoring during the study.
  - Participants who are HBsAg negative, HBcAb negative and HBsAb positive without documentation of prior HBV vaccination AND participants who are HBsAg negative, HBcAb positive, and HBsAb positive, will have HBV DNA assessed at screening.
    - If HBV DNA is detectable, participants will be excluded.
    - If HBV DNA is not detectable, participants may be eligible. If the participant is included in the study, for subsequent visits HBV DNA testing must be performed according to the [SoA](#).
3. History of autoimmune disorders.
  4. History of allergic or anaphylactic reaction to a therapeutic drug.
  5. History of recent active infections within 28 days prior to the screening visit.
  6. Participants with a fever within 7 days prior to dosing.

7. Infected with *Mycobacterium TB* as defined by any of the following:
  - A positive IGRA test performed at or within the 12 weeks prior to Day 1 is exclusionary; a negative test is required for eligibility. The following are acceptable IGRA assays: T-SPOT® TB test, QuantiFERON®-TB Gold In-Tube test (QFT-GIT), QuantiFERON®-TB Gold test (QFT-G) or QuantiFERON®-TB Gold Plus test (QFT-G Plus). In participants with a history of BCG vaccination, the IGRA test is strongly recommended since the Mantoux test (tuberculin, PPD skin test) may be positive due to vaccination.
  - If the results of the IGRA are indeterminate, the test may be repeated 1 time, and if a negative result is obtained, enrollment may proceed. A positive test on repeat is exclusionary.
  - A chest radiograph should be obtained if not done within the 3 months prior to screening. To be considered eligible for the study, the chest radiograph must be negative for active TB infection
  - History of either untreated or inadequately treated latent or active TB infection.
  - A participant who is currently being treated for active TB infection must be excluded from the study.
  - A participant who is being treated for latent TB infection can only be enrolled with exclusion of close contacts of multi-drug resistant TB, documentation of an adequate treatment regimen, and prior approval of the sponsor.
8. Contact with positive case of COVID-19 or travel to an area defined as high risk by relevant authority in the past 14 days.
9. Other medical or psychiatric condition including recent (within the past year) or active suicidal ideation/behavior or laboratory abnormality that may increase the risk of study participation or, in the investigator's judgment, make the participant inappropriate for the study.

